Cerebrovascular hemodynamics: 1) Cerebrovascular reactivity will be measured using Transcranial Doppler US by assessing the change in mean blood flow velocity of the middle cerebral artery (MFV_{MCA}) in response to a vasodilatory hypercapnic challenge (i.e. via CO₂ breathing) at baseline and 12 months.⁶⁵ An ultrasound probe will be positioned at the temporal window and held in place by an adjustable headband. This location offers an ideal exposure for Doppler ultrasonography of the middle cerebral artery since the temporal window is the thinnest part of the temporal bone. After baseline recordings at room air, subjects will breathe room air supplemented with 5% CO₂ to induce mild hypercapnia. Each condition is recorded for at least 5 minutes to achieve a steady state velocity. MFV_{MCA} will be determined for each condition by calculating the average velocity over each cardiac cycle for the last minute of each condition. ΔMFV_{MCA} will be calculated as: hypercaphic MFV_{MCA} – normocapnic MFV_{MCA} and used to compare cerebrovascular reactivity between sodium bicarbonate and placebo. Breath-by-breath end-tidal partial pressures of CO₂ (ETCO₂) will be continuously monitored and will be used to normalize the MFV_{MCA} response to changes in this arterial blood gas.⁶⁵ The assessment of ETCO2 is noninvasive and correlates strongly with (invasive) serial blood measures of arterial

blood gases.⁶⁵ The hypercapnia protocol used in this study has been used in the research setting for many years without any adverse events.⁶⁵⁻⁶⁷ Brachial arterial BP will also be measured during these assessments for correction due to any changes during hypercapnia. 2) Cerebrovascular Pulsatility Index and Resistance: Pulsatile cerebrovascular velocity will be determined using the Gosling Pulsatility index = $(MCA_{V(systolic)}, MFV_{MCA})$ and baseline and 12 months.⁶⁸ The mean, systolic and diastolic velocity of the MCA will be measured.

- 9-Hole Pegboard Dexterity Test (NIH Toolbox): This test records the time required for the participant to accurately place and remove 9 plastic pegs into a plastic pegboard. The protocol includes 1 practice and 1 test trial with each hand. Raw scores are recorded as time in seconds that it takes the participant to complete the task with each hand (a separate score for each).
- Grip Strength Test (NIH Toolbox): Participants are seated in a chair with their feet touching the ground. Participants are instructed to squeeze the Jamar Plus Digital Dynamometer as hard as they can for a count of three. A practice trial at less than full force and 1 test trial are completed with each hand.
- 30-second chair sit stand test: The patient will be seated in the middle of a chair with their hands on the opposite shoulder crossed at the wrists. Feet will be flat on the floor. On "Go", the patient will rise to a full standing position, then sit back down again. This will be repeated for 30 seconds and the number of times the patient stands in 30 seconds will be recorded. IF the patient must use his/her arms to stand, the test will be stopped and a 0 will be recorded for the number and score.
- 4-meter walk test: 4-meter walk test will be performed using protocol from NIH Toolbox. Patient will be asked to walk 4 meters at their usual pace. The patient will complete one practice and then two timed trials. The time in seconds to walk 4 meters on each of the two trials will be recorded. The test take approximately 3 minutes to administer.
- Physical Functioning Scale from the SF-36: Participants will complete the short questionnaire on their physical functioning. This is a validated scale that has been used in several CKD studies. The scale takes approximately 3-5 minutes to complete.
- Oxidative stress and inflammation: Oxidized LDL will be measured with Mercodia ELISA kit at the University of Colorado CTRC. Total antioxidant status will be measured at the CTRC with Randox Laboratories assay. C-reactive protein will be measured by immunoturbideimetric (Beckman Coulter) at the CTRC.
- Food frequency questionnaire (FFQ): This FFQ was developed for use in CKD/ESKD (end-stage kidney disease) to investigate highly/ultra-processed food consumption patterns that are typically high in sodium, potassium, and phosphorus. It was modified to include categories of alkaline fruits/vegetables and other acid/alkaline ash foods in the diet.

Justification for secondary outcomes: Transcranial Doppler Ultrasound is a noninvasive and safe way to examine cerebrovascular hemodynamics. Cerebrovascular reactivity (the vasodilation of cerebral arterioles in response to hypercapnia) is a surrogate marker of endothelial function in cerebral arteries and the pulsatility index is positively associated with arterial stiffness,⁶⁹ correlates with white matter hyperintensities,⁷⁰ and predicts cognitive impairment in patients.⁷⁰ Our research group has experience with these measurements ([name] and [name]) and [name] has established a cerebrovascular

laboratory in the KDRC. Oxidative stress has been identified as a key driver of aging and development of disease. Oxidative stress and inflammation are associated with cardiovascular pathophysiology and neurodegeneration.⁷⁸⁻⁸⁰ Several studies have found that oxidative stress and inflammation are associated with a decline in cognitive function.⁸¹⁻⁸³ Markers of oxidative stress and inflammation are increased in patients with CKD.⁸⁴⁻⁸⁵ Both oxidative stress and inflammation are associated with cardiovascular disease in CKD patients. Metabolic acidosis results in inflammation and oxidative stress.⁸⁶ Plasma oxidized LDL, IL1- β , IL-6, C-reactive protein and TNF- α have been shown to be higher in patients with CKD.⁸⁷⁻⁸⁸ Our laboratory has experience with these measurements.⁸⁹⁻⁹¹ The FFQ will inform if there were any changes in self-reported food consumption throughout the study. The FFQ will also inform if changes in study outcomes / measures were associated with changes in self-reported food consumption throughout the study (association, correlation, differences, confounding between study measures and outcomes). Additionally, it will be for participant stratification and for exploratory categorization of participants by self-reported foods consumed. This data will elude at categories of diets: alkaline, acidic, processed, high-sodium/potassium/phosphorus, and high-protein.

8. Power and Statistical Analysis: Briefly, in this pilot study a total of 50 patients will be enrolled and equally randomized to the two groups. The two-sample t-test is applicable to compare the change between the two groups for each cognitive function subdomain and is the basis for power analysis. This sample size was determined based on feasibility and availability, not a specified statistical power. With a two-sided type I error rate of 0.05, the study will have a power of 79% to detect an effect of 0.80 if 25 patients per group can be included in the final analysis. This power calculation applies to the secondary and other outcome variables. For Aim 1, we will assess the treatment effect on each of the six subdomains of cognitive function by a linear regression model with the measure at end of study regressed on treatment along with the baseline measure of the subdomain, sex, age, and baseline eGFR. Conclusion will be subdomain specific. For Aims 2 and 3, the linear regression model will be used to examine the treatment effect on the secondary and other outcomes. Particularly, the measure of an outcome variable at end of study will be regressed on intervention indicator and baseline measure of the outcome variable plus sex, age and baseline eGFR for adjustment purpose.

9. Potential Problems and Alternative Strategies

- Although subject recruitment and retention are always challenging, we should be able to complete the study in the proposed timeline given our groups excellent track record in recruiting participants in clinical trials.
- We should have few difficulties with the proposed experimental procedures and protocols as they are already established in the vascular laboratories at the KDRC by [name].
- We recognize that alternative approaches exist for examining the effects of alkali therapy on cognitive function in patients with CKD. For example, one alternative would be to undertake a larger study to examine structural changes with brain MRIs rather than the investigation proposed in the current application. However, our proposed study is the most cost-effective approach to obtain confirmation of the study hypotheses.

- We recognize that different dosages of sodium bicarbonate therapy can be used. However, the proposed dose in the current study has been shown to be safe and effective in treating metabolic acidosis in CKD 3-4.
- Systolic BP is an important determinant of vacular function and cognitive impairment and could be a theoretical confounder. However, we do not expect this to be an issue as all participants must have their BP controlled prior to entering the study and all patients must be on an ACEi or ARB or spironolactone. We will adjust for BP if differences in BP control is observed between the groups.
- We acknowledge that there may be other potential mechanisms by which acid retention results in cerebral vessel dysfunction. Acidosis induces inflammation and oxidative stress and net calcium and phosphate efflux from bone. We will collect plasma and serum to store for future analyses of these other mechanisms.

G. Summarize Knowledge to be Gained:

The new knowledge generated from this proposal will facilitate planning of future clinical trials in CKD patients that will aim to reduce the burden of cognitive dysfunction.

H. References: REFERENCES CITED

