Five cognitive summary scores were measured at baseline. Multivariate linear regression models were used to evaluate the cross-sectional association between serum bicarbonate and cognition. *Results:* The mean age (SD) and mean (SD) eGFR were 68 (8.5) years and 71 ml/min/1.73m², respectively. Global cognitive and executive functions were positively associated with serum bicarbonate (Table 1). These findings suggest that low bicarbonate levels may be detrimental to neuronal activity and support the need for an interventional trial examining whether correction of acidosis has a beneficial effect on cognitive function.

b) Bicarbonate administration results in improved vascular endothelial function (FMD) in patients with CKD stage 3b-4.⁴⁹ We performed a pilot, prospective, open label 14-week crossover study examining the effect of treatment of metabolic acidosis (defined by a low serum bicarbonate level of 16-22 mEq/L), with oral sodium bicarbonate therapy (dose 0.5 mEq/kg-lean body weight/day) in 20 patients with CKD stage 3b-4. The primary endpoint was change in FMD between treatment and control conditions. *Results:* The mean (SD) age and eGFR was 58.5 (12.8) years and 25.3 (8.3) ml/min/1.73m², respectively. The mean (SD) bicarbonate level increased after sodium bicarbonate therapy from 19.6 (2.9) mEq/L to 22.4 (3.0) mEq/L. BP control was similar between the two conditions. FMD significantly improved after 6 weeks of sodium bicarbonate therapy compared to control conditions (mean difference in %FMD 1.1% in the treatment arm vs. - 0.70% in the control arm, p=0.027), Figure 2. Bicarbonate therapy was well tolerated and there were no significant adverse events.

c) Feasibility of Aim 2 is demonstrated by our groups experience with cerebrovascular hemodynamics. In a small interventional trial of 8 adults over the age of 50 with baseline blood pressure >120 mmHg, 6 weeks of inspiratory muscle strength training (IMST) improved cerebrovascular reactivity compared to control.

	Δ CVR (Δ MCA _{velocity} / Δ end tidal CO2) from baseline Mean (SE)
IMST (Treatment Group) n=4	0.99 (0.31)
Control Group n=4	-0.14 (0.60)

IV. Research Methods

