- Baseline: During the baseline phase cognitive function, cerebrovascular hemodynamics, grip strength test, pegboard dexterity test, 30 second chair sit stand test, 4 meter walk test, physical functioning scale of the Short Form 36 (SF-36) serum basic chemistry panel, plasma oxidized LDL, total antioxidant status, IL1-β, IL-6, Creactive protein and TNF-α and venous blood gas will be performed and the GI symptom questionnaire will be assessed. Spot urine will be collected for albumin to creatinine ratio. Demographics, medical history and physical will be performed.
- Randomization: Participants will be randomized with a 1:1 allocation ratio to treatment and placebo group using block randomization. Block randomization will be based on sex, age (within 5 years) and CKD stage (3b or 4). List of randomization will be generated by the study statistician and sent to the study pharmacist (A) Green Mountain Pharmaceutical, Denver, CO, and/or B) University of Colorado Research Pharmacy) blinded to the PI. Study investigators, healthcare providers, participants, data collectors, outcome adjudicators and data analysts will be blinded to treatment assignment.

- Follow-up: The follow-up schedule includes:
 - 1, 2, 4, 5, 7, 8, 10, and 11 months: safety check-in call via phone to complete adverse event assessment and GI symptom questionnaire
 - 3 and 9 months: safety visit (basic chemistry panel, adverse event assessment, GI symptoms questionnaire, BP, pill compliance).
 - 6 months: 1) Adverse event assessment, GI symptoms questionnaire, BP, pill compliance; 2) outcome measures: cognitive function, grip strength test, pegboard dexterity test, 30 second chair sit stand test, 4 meter walk test, physical functioning scale of the SF-36, serum basic chemistry panel, plasma oxidized LDL, total antioxidant status, IL1-β, IL-6, C-reactive protein and TNF-α; 3) spot urine for albumin to creatinine ratio.
 - 12 months: 1) Adverse event assessment, GI symptoms questionnaire, BP, pill compliance; 2) outcome measures: cognitive function, cerebrovascular hemodynamics, grip strength test, pegboard dexterity test, 30 second chair sit stand test, 4 meter walk test, physical functioning scale of the SF-36serum basic chemistry panel, plasma oxidized LDL, total antioxidant status, IL1-β, IL-6, C-reactive protein and TNF-α and venous blood gas; 3) spot urine for albumin to creatinine ratio.

Table 1		
Inclusion Criteria	Exclusion Criteria	

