Rationale for sodium bicarbonate dose: A dose of 0.5 mEq/kg-LBW/day has been shown to be safe and effective for treatment of metabolic acidosis in patients with CKD.^{49,53-54} Previous studies using this dose of sodium bicarbonate have not reported significant changes in edema, body weight or BP.^{49,53-55} In our **preliminary data**, sodium bicarbonate administration was not associated with an increase in BP or fluid gain in patients with CKD stage 3b-4.⁴⁹ Additionally, we will dose sodium bicarbonate based on LBW, not actual body weight. The volume of distribution of bicarbonate is approximately that of total body water. Total body water is dependent on lean body mass. Standard equations will be used to determine LBW.⁵⁶

b) Placebo: Subjects randomly assigned to placebo will take the same number of capsules as if they were assigned to receive 0.5 mEq/kg-LBW/day of sodium bicarbonate. Participants will take ½ the daily dose in the morning and the other ½ in the evening. The number of capsules will be rounded to the nearest whole capsule. To reduce pill burden and increase compliance the maximum number of pills per day will be six.

Rationale for placebo: A placebo group is necessary to successfully complete our aims. If a placebo group were not included both the investigators and participants would know that they are receiving sodium bicarbonate, which could influence medical management and perception of side effects in the study.

Dose Titration of Study Drug: If at month 3 the serum bicarbonate level not $\ge 23 \text{ mEq/L}$, we will increase the dose of sodium bicarbonate to 0.8 mEq/kg/LBW. This dose was recently used in a randomized trial comparing the safety and efficacy of doses of sodium bicarbonate therapy and was found to be well tolerated without any significant differences in adverse events or hospitalization compared with placebo.⁵⁷

5. Rationale for study duration. Changes in cognitive function, cerebrovascular reactivity and pulsatility can be seen within 4-6 weeks in adults 50 years and older but may require longer periods of time and published data use a period of 3 months to 1 year.⁵⁷⁻⁶¹ Hence, we are proposing a 12-month intervention.

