5. Safety monitoring: Sodium bicarbonate therapy may cause bloating, flatulence and abdominal discomfort. Although previous studies using similar doses of sodium bicarbonate have not reported significant changes in edema, body weight or BP,^{49,53-55} sodium bicarbonate may cause edema to develop or worsen thereby increasing BP. Sodium bicarbonate also has the potential for causing metabolic alkalosis and hypokalemia if it is retained rather than excreted in the urine. These expected adverse events will be monitored during the study. Serum bicarbonate may fall due to natural progression of CKD, particularly in the placebo group. Rescue therapy with open-label sodium bicarbonate will be initiated if serum bicarbonate is <16 mEq/L on 2 consecutive measurements until the serum bicarbonate is ≥ 16 mEq/L. Participants will not discontinue study medications if open-label sodium bicarbonate is prescribed. Please see the protection of human subjects section for full safety monitoring details.

Medical Supervision and Subject Surveillance. The Kidney Disease Research Center nursing staff will have the responsibility of performing blood draws from participants. The vascular technician will have the responsibility of performing the cerebrovascular function measurements under the supervision of [name] Director of the Vascular Biology Lab at the University of Colorado Anschutz Medical Campus. The research study coordinator will be responsible for performing the cognitive function tests and for collecting information about treatment adverse events. [name], the PI, will be responsible for supervision of the entire study. [name] will make final decisions regarding subject screening/enrollment and monitor/oversee clinical status and subject safety.

a) Data Safety Monitoring Plan. To ensure the safety of subjects, they will need to meet rigorous inclusion/exclusion criteria, including comprehensive health screening procedures. The participants' personal physicians will also be informed of their patients' participation in the study.

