• **Expected adverse events:** Sodium bicarbonate therapy may cause bloating, flatulence and abdominal discomfort. Although previous studies using similar doses of sodium bicarbonate have not reported significant changes in edema, body weight or BP,^{49,53-55} sodium bicarbonate may cause edema to develop or worsen thereby increasing BP. As shown in our preliminary data, sodium bicarbonate did not result in increased BP.⁴⁹ Sodium bicarbonate also has the potential for causing metabolic alkalosis and hypokalemia if it is retained rather than excreted in the urine. These expected adverse events will be monitored during the course of the study and in general, can be medically managed by

adjusting antihypertensive and/or diuretic agents, providing potassium replacement and by dietary changes. Of note, none of these adverse events were observed in our previous short-term pilot study. Patients will have safety visits and check-in calls to assess side effects and check laboratory values.

• Dose reduction and discontinuation:

- Serum bicarbonate >28 mEq/L: The intervention dose (study drug) will be reduced by 50% and diuretics will be adjusted as appropriate. The participant will return for a visit one week later to have serum chemistries rechecked. If the bicarbonate remains >28 mEq/L the intervention will be stopped and the participant will have serum bicarbonate measured weekly until it is <28 mEq/L. PI will monitor for symptoms of hypocalcemia as an increase in pH can decrease the ionized calcium concentration.^{117,118} Management of low calcium will be at the discretion of the PI based on symptoms reported by the patient.
- Systolic blood pressure ≥ 160 mmHg or diastolic blood pressure ≥ 90 mmHg: Potential reasons for uncontrolled BP, such as poor compliance or running out of medications will be evaluated and managed appropriately. If an identifiable cause is not found, the PI will increase anti-hypertensive medications and/or diuretics. The participant will return 1 week later for follow-up. If BP remains >160/90 mmHg at the second visit, medications will again be increased and the intervention dose will be reduced by 50%. The participant will return 1 week later. If BP remains unchanged at the third visit, the intervention will be stopped and medications will again be escalated. Participants will continue to have PRN visits weekly until BP is <160/90 mmHg.

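### The blinding statement covers investigators and data collectors, but the study team acts on serum bicarbonate, the drug's direct readout, and no masking of it is described

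*Combined protocol and SAP*

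**What the plan says.** The Randomization paragraph (IV. Research Methods) sets the blind: "Study investigators, healthcare providers, participants, data collectors, outcome adjudicators and data analysts will be blinded to treatment assignment". Under Study Drug Dosing, the rationale for placebo explains its purpose. Without a placebo group, investigators and participants would know the treatment, "which could influence medical management and perception of side effects in the study".

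Three rules act on serum bicarbonate:

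- **Month 3, not yet at 23 mEq/L:** a dose increase (Dose Titration of Study Drug).
- **Above 28 mEq/L:** "The intervention dose (study drug) will be reduced by 50% and diuretics will be adjusted as appropriate" (Dose reduction and discontinuation).
- **Below 16 mEq/L on two consecutive measurements:** open-label rescue (Safety monitoring; Dose reduction and discontinuation).

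The follow-up schedule has a chemistry panel at months 3, 6, 9 and 12. A venous blood gas is taken at baseline and month 12.

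The protocol gives the principal investigator clinical and safety oversight, day-to-day monitoring, watching for hypocalcemia under the above-28 rule, increases in antihypertensives or diuretics, the judgement of severe edema, and exits for side effects. The research coordinator gives the cognitive tests and also collects adverse events. A vascular technician makes the Doppler measurements.

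On the expected direction of bicarbonate, Safety monitoring says: "Serum bicarbonate may fall due to natural progression of CKD, particularly in the placebo group".

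**The concern.** Bicarbonate is what the drug is given to raise, so a clinician who sees a participant's values has evidence about the arm. If that clinician also chooses co-treatment, grades edema and decides exits, those choices can differ by arm without anyone having seen the list. Blood pressure and the set of participants still present at month 12 both feed the cognitive and Doppler comparisons. With 25 per group and no stated allowance for dropout, a few arm-related exits would matter.

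The titration text raises a related problem. The increase is worded for sodium bicarbonate, while placebo capsules are matched only to the starting dose. Read literally, a dose step would raise the capsule count in the active arm alone. Participants could then see the arm, and so could staff checking pill compliance.

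**Working it through.** **The plan's own figure.** Power and Statistical Analysis states: "With a two-sided type I error rate of 0.05, the study will have a power of 79% to detect an effect of 0.80". That section makes the figure conditional on analysing all 25 participants in each arm. For a two-sample t-test, df = 48 and the noncentrality is 0.80 × √(25/2) = 2.83, which gives power 0.791. The stated 79% reproduces, and nothing below changes it.

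**How much bicarbonate reveals: inputs.**

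- Preliminary Studies, b): "The mean (SD) bicarbonate level increased after sodium bicarbonate therapy from 19.6 (2.9) mEq/L to 22.4 (3.0) mEq/L". The 22.4 (SD 3.0) stands in for active and the 19.6 (SD 2.9) for placebo. This is a proxy, because it is a before-and-after change on treatment. Bicarbonate under the pilot's control condition is not given.
- Allocation: "Participants will be randomized with a 1:1 allocation ratio to treatment and placebo group using block randomization". Guessing at random is therefore right 50% of the time.
- Assumed: normal distributions and, for repeated values, a constant within-patient correlation ρ of 0.3 to 0.7. The documents give no correlation.

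**One month-3 value.**

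- Pooled SD = √((2.9² + 3.0²)/2) = 2.95.
- D = 2.8/2.95 = 0.949.
- Best-guess accuracy = Φ(D/2) = Φ(0.475) = 0.682.
- AUC = Φ(D/√2) = Φ(0.671) = 0.749.

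**At the titration cut-off of 23.**

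- P(≥23) on placebo = 1 − Φ(3.4/2.9) = 0.121. On active it is 1 − Φ(0.6/3.0) = 0.421.
- P(active given ≥23) = 0.421/(0.421 + 0.121) = 0.78.
- P(placebo given <23) = 0.879/(0.879 + 0.579) = 0.60.
- Share of all participants below 23 = (0.879 + 0.579)/2 = 0.73.

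**Baseline plus k follow-up values.** D = 0.949/√[(1 + (k − 1)ρ)/k − ρ²], and accuracy = Φ(D/2).

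| ρ | Baseline + month 3 | Baseline + months 3, 6, 9 |
|---|---|---|
| 0.3 | 0.691 | 0.762 |
| 0.5 | 0.708 | 0.769 |
| 0.7 | 0.747 | 0.803 |

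Month 12 is left out because a value drawn at the final visit cannot drive decisions before the endpoint.

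**Sensitivity.** With a shift of only 1.5, one value gives 0.600. With a shift of 2.8 and SD 2.0, it gives 0.758. For baseline plus three visits, shifts of 1.5 or 2.8 with SDs of 2.95 or 2.0 give about 65% to 90%.

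**Safety thresholds, single reading.**

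- P(<16) = 10.7% on placebo and 1.6% on active.
- P(>28) = 0.2% on placebo and 3.1% on active.
- Either threshold: 10.7 + 0.2 = about 11% on placebo; 1.6 + 3.1 = about 5% on active.

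**The case against.** The strongest reply is that the link from value to decision-maker is not written down. The titration rule says only that the team will act, the above-28 and below-16 rules are in the passive, and none names who reads the result. Safety monitoring refers to a human-subjects section for full details. That section is not in the text available and could contain a masking step. This stands. It is why the investigator's access has to be called an inference, although the monitoring and hypocalcemia duties make it a reasonable one.

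The plan also narrows the room for discretion. Dose changes for blood pressure and potassium follow numeric triggers. Blood pressure is taken in triplicate on an automated device. The run-in is there to keep later antihypertensive changes few, and Potential Problems and Alternative Strategies plans an adjustment if blood pressure control differs between groups. These limit the problem but do not remove it. Choice of drug, edema grading and exits remain matters of judgement, and adjusting for blood pressure measured after randomisation does not undo arm-related co-treatment or exits.

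The size rests on a weak proxy. Regression to the mean may account for part of the 2.8, and rescue in the placebo arm or poor adherence would narrow the gap. In the other direction, an SD of 2.9 is wide for a 16 to 22 entry window, and titration could widen the gap. Even on the pilot figures, about 73% of participants fall below 23 at month 3, where a guess of placebo is right only 60% of the time.

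Finally, the rationale for placebo speaks of investigators knowing the treatment, which is more than a probabilistic guess. The trial is also a pilot sized on feasibility.

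**Conclusion.** The point holds in a limited form. The blinding statement is broader than the described procedures support, because the team acts on the drug's direct readout and the available text describes no masking of it. On the pilot proxy, one value identifies the arm about 68% of the time, and baseline plus three visits about 76% to 80%, against 50% by chance. The repeated-visit range rests on assumed correlations, and both figures rest on reading a before-and-after change as a between-arm difference.

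A reader might infer that the principal investigator is in effect unblinded. The documents do not show that: the reader of the result is not named, and the information is well short of certain. A reader might also infer that the cognitive results are biased. That is not shown either. The Toolbox tests are computerised, nothing says that the coordinator sees the chemistry results, and no effect on any outcome can be estimated. The possible route is through discretionary co-treatment, edema and exit decisions before month 12. Titration itself is a month-3 step, not one repeated at every visit.

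This should be corrected, with moderate confidence.

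**What to change.** 1. **Reconcile the titration text first.** Dose Titration of Study Drug and the placebo paragraph must be brought into line with the double blind in the Randomization paragraph, so that a dose step does not reveal the arm through capsule count. No dose or threshold is proposed here. Routing results to someone who holds the list, with the text as it stands, could make matters worse.
2. **Mask the outcome testers.** State that post-randomisation bicarbonate and the month-12 blood gas are withheld from the coordinator who gives the cognitive tests and from the vascular technician.
3. **Route routine values, where feasible, to the research pharmacist**, who already receives the randomisation list. The principal investigator gets the rest of the panel, plus an alert whenever an existing protocol safety threshold is crossed. Where the outside pharmacy supplies the drug, a route for results has to be agreed.
4. **Name who reads bicarbonate results.** If the human-subjects section already sets a masking step, repeat it beside the blinding statement. If the principal investigator must keep seeing the values, qualify that statement to say so.

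The cost is a filtered laboratory report, a pharmacy worksheet and pharmacist time. The principal investigator would not see routine values between alerts, which is a trade-off in oversight for the sponsor and the DSMB to accept or decline. Some leakage remains, since on the pilot figures a single reading would trigger an alert in about 11% of placebo and 5% of active participants.
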